**Table 26: Planned Pharmacokinetic Parameters by Matrix and Study Day**

Parameter	Definition	Calculation
SAD, Study Day 1, Serum PK Parameters		
C max	Maximum serum concentration	Observed
T max	Time of maximum serum concentration	Observed
AUC last	Area under the concentration-time curve from 0 to the last quantifiable serum concentration	Linear-Log trapezoidal method
AUC inf	Area under the concentration-time curve from 0 extrapolated to infinite	Calculated as AUC 0-last + C est,last /λ z , where C est,last is the estimated last measurable concentration
T 1/2	Apparent terminal elimination half-life	ln(2)/λ z , where λ z is the apparent first-order terminal elimination rate constant.
λ z	Terminal elimination rate constant	Log-linear regression of the concentration-time curve during terminal elimination
Cl/F	Apparent Clearance	Dose/AUC inf
V d /F	Apparent volume of distribution	Dose/AUC inf * λ z
SAD, Study Day 1, Urine PK Parameters		
A e	Amount excreted unchanged in the urine	Cumulative: Sum of concentration* volume per collection interval
Fe%	Fraction of Dose excreted	Calculated as A e /Dose, where A e is the amount of unchanged drug excreted in urine during a collection

	unchanged in the urine	interval and D is the Dose
Clr	Renal Clearance	Calculated as $Ae_{24}/AUC_{24}$ where Ae is the amount of unchanged drug excreted in urine during the first 24 hours post-dose and $AUC_{24}$ is the Area under the concentration versus time curve from 0 to 24 hr.
MAD, Week 1, Dose 1, Serum		
Cmax	Maximum serum concentration	Observed
Tmax	Time of maximum serum concentration	Observed
AUCtau	Area under the concentration-time curve from 0 to the end of the dosing interval (tau, where tau will equal 48 hours).	Linear-log trapezoid
MAD, Week 4, Dose 12, Serum		
Ctrough	Trough serum concentration	Observed
Cmax	Maximum serum concentration	Observed
Tmax	Time of maximum serum concentration	Observed
AUCtau *	Area under the concentration-time curve from 0 to the end of the dosing interval (tau, where tau will equal 48 hours).	Linear-log trapezoid
Css	Steady-state concentration	$AUC_{tau}/tau$ , where tau will equal 48 hours

Ro	Accumulation ratio	AUCtau (week 4, dose 12)/ AUCtau (week 1, dose 1)
Ro,Cmax	Cmax, accumulation ratio	Cmax(week 4, dose 12)/ Cmax (week 1, dose 1)
Accumulation Index	Estimated accumulation index	$1/(1 - e^{-\lambda * \text{tau}})$
CL/F	Apparent clearance	Dose/AUCtau
V/F	Apparent volume	Dose/AUCtau* $\lambda z$

\*Sampling collection scheme during week 4, dose 12 allows for sample collection windows. The 96-hr sample time collection may occur between 48 and 144 hours post dose. For samples in which C48 was collected, AUCtau will be generated using observed data. For samples in which C48 was not collected, C48 will be estimated using each subject's individually estimated  $\lambda$  from week 4, dose 12, provided there is sufficient data to estimate the elimination rate constant. Data will be considered sufficient if there are no less than 3 time points included in the estimation, R-squared values are at least 0.9, and the percent of data extrapolated is less than 20%.

Concentrations below the limit of quantification (BQL) will be considered to be 0 concentration. With the possible exception of C48 (week 4, dose 12), missing values will not be imputed. If sufficient data are missing for a given subject, that subject may be considered non-evaluable for pharmacokinetic analysis and will not be included in the PK Population.

All serum, urine and sputum concentration data and the per-subject pharmacokinetic parameters will be displayed in listings. Summary statistics will be generated for each pharmacokinetic parameter unless there are less than three subjects will evaluable data. Summary statistics will include mean, median, geometric mean, standard deviation, minimum, maximum, and percentage of coefficient of variation. Concentration-time profiles will be plotted by individual and mean concentration-time profiles will be plotted by dose and study day on both the log and linear scales (if applicable). Dose-normalized parameters will be plotted for dose-ranging studies. Because there may be a relationship between pseudomonas and QR-010 systemic exposure, summary statistics and descriptive figures may also be generated by day, dose and pseudomona at the discretion of the team, but no formal statistical analysis will be performed and these additional tables and figures will be excluded from the top line report.

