7.1 Visit and Assessment Windows

The flexibility regarding scheduling of study days and corresponding procedures differ depending on the cohort and phase of the study. The timing of assessments, procedures and sample collections outlined in the protocol are nominal times. It is understood that in the phase 1 setting, actual times will approximate rather than match the nominal times exactly. Actual times are to be recorded in the source documentation and in the case report forms (CRFs), and, if any time points are missed, the reasons are also recorded.

For the SAD cohorts, there is no flexibility regarding the timing of the scheduled study days in relation to dose Day 1.

For the MAD cohorts, there is some flexibility regarding the timing of the scheduled study days in relation to dose Day 1. The description of procedures assumes a Monday-Wednesday-Friday dosing schedule. An alternative dosing schedule can be used, provided that there is at a minimum 2 days between doses, and a maximum of 4 days between doses. Missed doses are to be recorded as such, and the overall treatment period should remain at 4 weeks, and not be extended to accommodate the missed doses. Missed doses are to be recorded in the CRF.

Details regarding acceptable windows for timing of study procedures for both the SAD and MAD cohorts can be found in the Laboratory Manual.

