13.8 Pharmacokinetics Analyses

To determine the PK profile of inhaled administrations at the different dose levels of QR-010, the following PK parameters will be calculated if sufficient data are available for each dose:

- C_{max} : The maximum serum concentration will be taken directly from the data.
- T_{max} : Time to C_{max} will be taken directly from the data.
- $T_{1/2}$: The terminal elimination half-life will be estimated by non-linear regression analysis of the terminal elimination slope, if feasible.
- AUC_{0-t} : Area under the curve to the final sample with a concentration greater than lower limit of quantification (LLQ) will be calculated using the linear trapezoidal method.
- $AUC_{0-\infty}$: Area under the curve to infinity will be calculated based on the last observed concentration $C_{last}(obs)$ using formula: $AUC_{0-\infty} = AUC_{last} + C_{last}(obs)/\lambda_z$, if feasible.
- CL: Serum clearance will be estimated using the formula: $CL = Dose/AUC_{0-\infty}$.

Achievement of steady state of the drug will be determined from trough levels.

Exact procedure for imputation of data will be described in the SAP.

All samples obtained from all cohorts will be analyzed to avoid bias in data presentation.

Sparse sampling analysis may be used to mitigate the risk of insufficient data to create individual profiles. The same approach may be used for non-compartmental analysis of sputum concentrations. This option provides the opportunity to characterize drug PK in CF patients as thoroughly as possible while keeping blood draws to a reasonable minimum for ethical considerations.

Correlation between concentrations in different matrices (serum, urine, sputum) may be explored.

Drug concentrations will be summarized by nominal time point if 3 or more values are available. Descriptive statistics for PK parameters will be performed if $\geq 50\%$ of subjects have evaluable data and number of values to summarize is ≥ 3 .

Geometric means and coefficients of variation will be tabulated for C_{\max} , AUC_{0-t} , $AUC_{0-\infty}$ and CI for each dose group if possible. T_{\max} will be summarized by median, minimum and maximum. Mean, standard deviation, minimum and maximum will be provided for $T_{1/2}$. Exact details for statistical analysis of PK concentrations and derived PK parameters will be presented in SAP.

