**Table 5: Target Visit/Days for MAD**

Dose (Visit)	Expected date EXPDATE (Dose n-1 date + expected number of days)	Target Dose Visit Date
Dose 1 (Day 1)	Day 1	Dose 1 date
Dose 2 (Day 3)	Dose 1 date + 2 days (i.e. 3-1), time 00:00	
 
• If any dose within expected date +/-1 days then = this dose date,
 
• else = expected date (i.e. = Dose 1 date + 2 days)
 

Day 4	Day 3 Target date+1 day	Day 3 Target date+1 day
Dose 3 (Day 5)	Day 3 Target date + 2 days (5-3), time 00:00	
 
• If any dose within expected date +/-1 days then = this dose date,
 
• else = expected date (i.e. Day 3 Target Date + 2 days)
 

Dose 4 (Day 8)	Day 5 Target date + 3 days (8-5), time 00:00	"
Dose 5 (Day 10)	Day 8 Target date + 2 days, time 00:00	"
Dose 6 (Day 12)	Day 10 Target date + 2 days, time 00:00	"
Dose 7 (Day 15)	Day 12 Target date + 3 days, time 00:00	"
Dose 8 (Day 17)	Day 15 Target date + 2 days, time 00:00	"
Dose 9 (Day 19)	Day 17 Target date + 2 days, time 00:00	"
Dose 10 (Day 22)	Day 19 Target date + 3 days, time 00:00	"
Dose 11 (Day 24)	Day 22 Target date + 2 days, time 00:00	"
Dose 12 (Day 26)	Day 24 Target date + 2 days, time 00:00	"
Day 33	Day 26 Target date + 7 days	Day 26 Target date + 7
Day 54	Day 26 Target date + 28 days	Day 26 Target date + 28

For time points with time precision relative to dose (i.e. "Dose time+ XX min"), the time is computed with respect to the end time of dosing (end of inhalation).

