#### **4.9. Pharmacokinetic Evaluations**

In the SAD portion of the study, sample collections for support of PK analysis are planned as follows:

- Blood (i.e. serum): pre-dose (time 0), 0.5, 1, 2, 3, 4, 12, 24, 48, 54, 72, 168 hours post-dose.
- Urine: Pre-dose (time 0); Pooled from 0 to 4, 4 to 12, and 12 to 24 hours post-dose; and 48, 72, and 168 hours post dose.
- Sputum: 3 samples obtained within first 6 hours post dose; 24 hours post dose; Day 4 (72 hours post dose); and Day 8 (168 hours post dose)

In the MAD portion of the study, sample collections for support of PK analysis are planned as follows:

Week 1, Dose 1

- Serum: 0, 0.5, 1, 2, 3, 4, 12; pre-Dose 2 (48 hours post-dose 1)
- Urine: Pre-dose; Pooled from 0 to 4 and 4 to 12 hours post Dose 1.
- Sputum: pre-dose, 3 samples obtained within first 6 hours post Dose 1.

Week 4, Dose 12

- Serum: pre-dose (0), 1, 2, 3, 4, 8, 24, 96, 144 (7 days post-last dose) and 648 hours (28 days post-last dose).
- Urine: Pre-dose; 24 and 96 hours, post-dose.

Additional sample collections are planned on interim study days during the MAD portion of the study. The measured concentrations will be presented in listings and used to confirm adequate QR-010 exposure; however, they will not be used to support generation of PK parameters. Additionally, urine concentrations that did not come from pooled collections or for which sample volumes were not collected will only be displayed in listings and will not be used to support generation of renal PK parameters.

The planned PK parameters for each portion of the study may be found in Table 26 below. Area under the serum concentration curve (AUC) will be generated using the linear-log trapezoidal rule.

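### SAP Table 26 treats dose 12 as the end of uniform 48 h dosing at steady state, but the schedule is 48/48/72 h, so Css (short half-life) or CL/F and the accumulation index (long half-life) are overstated; both V/F rows also lack a bracket

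*SAP*

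**What the plan says.** SAP Table 26 gives the dose-12 AUCtau as "Area under the concentration-time curve from 0 to the end of the dosing interval (tau, where tau will equal 48 hours". From it the table derives Css as AUCtau/tau with the same 48 h, CL/F as Dose/AUCtau, and an accumulation index of 1/(1 - e^(-λ·tau)).

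The dosing schedule is not uniform. SAP Table 5 sets the dose 4 visit at "Day 5 Target date + 3 days (8-5), time 00:00", and the 3-day step recurs before doses 7 and 10. Protocol 7.1 assumes Monday-Wednesday-Friday dosing and allows alternatives "provided that there is at a minimum 2 days between doses, and a maximum of 4 days between doses".

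On steady state, protocol 13.8 says: "Achievement of steady state of the drug will be determined from trough levels". It gives no criterion, and it defines clearance as Dose/AUC0-∞. SAP 4.9 lists the interim multiple-dose concentrations and uses them to confirm adequate exposure, but says "they will not be used to support generation of PK parameters". No row of Table 26 depends on a steady-state finding.

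The single-dose volume row reads "Dose/AUC inf * λ z". The multiple-dose row has the same form, with AUCtau in place of AUCinf.

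**The concern.** AUC over a dosing interval divided by its length is the average steady-state concentration, and Dose/AUCtau is clearance, only if every interval equals tau and steady state has been reached. Here every third interval is 72 h, and dose 12 (Day 26) sits in the Friday slot, which this schedule normally follows with 72 h. Steady state is assumed without being made a condition.

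The stake is interpretation of secondary pharmacokinetic results. A quantity labelled Css could be read as the average exposure of the regimen, and one labelled CL/F as clearance, when one or the other is systematically too high. V/F calculated as typed would not be a volume.

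**Working it through.** **Inputs.** tau = 48 h (SAP Table 26). Dose days 1, 3, 5, 8, 10, 12, 15, 17, 19, 22, 24, 26 (SAP Table 5). Half-life is not given in either document, so a range is assumed. The model is one compartment.

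**Where 48 h comes from.** The gaps between the 12 doses are 48, 48, 72, 48, 48, 72, 48, 48, 72, 48, 48 h. So 48 h is correct for the interval after dose 1, and for 8 of the 11 gaps. Over a full week the mean interval is 168/3 = 56 h.

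**AUC0-48 after the Friday dose at steady state.** Earlier doses were given 48, 96, 168, 216, 264, … h before. The 0-48 h window therefore collects 144 of every 168 h of the single-dose curve:

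AUC0-48 = (Dose/CL)·r, with r = (1 - e^(-144λ))/(1 - e^(-168λ)).

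r lies between 144/168 = 0.857 (very long half-life) and 1 (short half-life).

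**Errors at steady state.**
- Reported CL/F ÷ true CL/F = 1/r.
- The weekly mean concentration is 3·Dose/(168·CL) = Dose/(56·CL), so reported Css ÷ weekly mean = r·56/48.
- The index for this schedule is (1 + e^(-48λ) + e^(-96λ))/(1 - e^(-168λ)). The SAP formula divided by this is again 1/r.
- Reported CL/F × reported Css = Dose/48 always; the true product is Dose/56. The product is 56/48 = 1.167 times too high at any half-life. Half-life only decides where the 16.7% falls.

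**After 12 doses (4 weeks).** r is multiplied by (1 - e^(-672λ)).

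Example at 48 h: e^(-144λ) = 0.125 and e^(-168λ) = 0.0884, so r = 0.875/0.9116 = 0.960. CL/F is 1/0.960 = 1.042 times true; Css is 0.960 × 1.167 = 1.120 times the weekly mean.

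| Assumed half-life (h) | r | CL/F and index, steady state | Css, steady state | CL/F after 12 doses | Css after 12 doses* |
|---|---|---|---|---|---|
| 12 | 0.9998 | 0.0% | +16.6% | 0.0% | +16.6% |
| 24 | 0.9921 | +0.8% | +15.7% | +0.8% | +15.7% |
| 48 | 0.9598 | +4.2% | +12.0% | +4.2% | +12.0% |
| 72 | 0.9357 | +6.9% | +9.2% | +7.0% | +9.0% |
| 168 | 0.8959 | +11.6% | +4.5% | +19.1% | -2.0% |
| 336 | 0.8775 | +14.0% | +2.4% | +52.0% | -23.2% |

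*Against the true steady-state weekly mean.

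**Index at 168 h.** SAP formula: 1/(1 - 0.820) = 5.6. Schedule at steady state: 5.0. Sum over the 12 actual doses: 4.7.

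**V/F.** Dose/AUC is clearance (volume per time). Read left to right, the typed entry multiplies it by λz (per time) and gives volume per time squared. A volume is Dose/(AUC × λz).

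**The case against.** Several objections have force.

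- A reader might infer that all three parameters are about 17% wrong. They are not: the maxima fall at opposite ends. Css is worst when CL/F is nearly exact, and CL/F approaches 17% at steady state only for half-lives too long for steady state by dose 12. Where 95% of steady state is reached by dose 12 (half-life up to about 155 h), the schedule alone biases CL/F and the index by at most about 11%.
- A reader might infer that the interim troughs are merely listed. SAP 4.9 also uses them to confirm exposure, and protocol 13.8 plans a trough assessment. The gap is narrower: no criterion, and no link to Css or CL/F.
- It is tempting to call these headline results that would distort a comparison of clearance between single and multiple dosing. Neither is in the plan. Css and the index appear in neither protocol 10.1 nor 13.8, SAD and MAD outputs are separate, and analysis is descriptive in about six active subjects per dose.
- It is tempting to put a fold-error on V/F. None exists, because the typed result has different units. It is probably a missing bracket that validated software would not reproduce.
- Scaling CL/F by r is a tempting repair, but it can do harm. Assume a two-phase profile with 80% of AUC at a 4 h half-life and 20% at 168 h. Unscaled CL/F is then +2.1% off at steady state; scaled, it is -8.5% off. If an allowed schedule puts the 72 h gap just before dose 12, scaling still leaves +14% at a 48 h half-life and +12% at 72 h. In the same two-phase profile true AUC accumulation is 1.17, far below either one-compartment index, so any predicted index is a weak measure.

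These points limit the size and importance of the problem and shape the remedy. None makes the 48 h formulas fit a 48/48/72 h schedule.

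**Conclusion.** The concern holds in this limited form. On the planned schedule, AUC0-48/48 is not the regimen's average steady-state concentration: it is too high by up to 17% at short half-lives, 12% at 48 h and 4.5% at 168 h. CL/F and the accumulation index are close to right at short half-lives and overstated by 4% at 48 h and 12% at 168 h. Without steady state, CL/F is overstated further, by 19% at 168 h and 52% at 336 h.

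These figures assume one compartment and Monday-Wednesday-Friday dosing. With no half-life in the documents, they bound the error and do not estimate it; for CL/F it may be negligible. AUC0-48 is a valid partial area, Cmax is untouched, and Ro compares like windows. Both V/F rows need a bracket. Only secondary pharmacokinetic parameters are involved; safety and MTD conclusions are unaffected.

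**What to change.** Amend SAP Table 26:

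- **Css.** Rename AUCtau/48 as *average concentration 0-48 h after dose 12*.
- **CL/F.** Report Dose/AUC0-48 as CL/F only for subjects whose pre-dose troughs, each taken after an actual 48 h interval, are quantifiable and meet a stated numeric plateau criterion. On the Monday-Wednesday-Friday schedule, the troughs before doses 6, 9 and 12 are like for like and already scheduled. Requiring quantifiable values matters because the SAP sets values below quantification to 0, so undetectable troughs would otherwise pass. Footnote that the formula assumes equal 48 h intervals and may overstate CL/F when half-life is long. Otherwise report AUC0-48 only. Apply no one-compartment correction factor.
- **Accumulation.** Make the observed Ro the main measure. Compute the predicted index from each subject's actual dose times, as the sum over doses i of e^(-λ·(time of dose 12 - time of dose i)), labelled as a one-compartment prediction.
- **V/F.** Write Dose/(AUC × λz) in both the SAD and MAD rows. The MAD row inherits any CL/F error, so give it the same condition and footnote.

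The cost is table wording and a few lines of programming on data already collected. The downside is that CL/F will not be reported for some subjects.

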7.4.10 Follow-up Visit for PK—24 hours +/- 12 hours After Last Dose

Subject to return to clinic to obtain serum and urine samples for PK. The samples can be collected any time within the time window specified.

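### The dose-12 AUCtau rule in the SAP Table 26 footnote discards usable values: C48 depends on lambda-fit and extrapolation criteria even when samples bracket 48 h

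*SAP*

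**What the plan says.** Table 26 defines AUCtau after dose 12 over 0 to 48 h. Css, Ro and CL/F are computed from it directly, and V/F from it together with λz. Dose-12 serum is planned at "pre-dose (0), 1, 2, 3, 4, 8, 24, 96, 144 (7 days post-last dose) and 648 hours (28 days post-last dose" (SAP 4.9), so no 48 h sample is scheduled. The footnote adds: "The 96-hr sample time collection may occur between 48 and 144 hours post dose". Protocol 7.4.10 puts the preceding sample at "24 hours +/- 12 hours After Last Dose".

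If a 48 h sample exists, "AUCtau will be generated using observed data". If it is missing, the footnote has C48 calculated from the subject's own dose-12 lambda, but only when the data suffice. The fit must rest on three or more points, and two further limits apply: "R-squared values are at least 0.9, and the percent of data extrapolated is less than 20" percent. The denominator and starting point of that percentage are not given. Apart from C48, missing values are not imputed, so a subject who fails has no stated route to a dose-12 AUCtau.

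Three other provisions matter. Values below the quantification limit are set to zero. A parameter with fewer than three evaluable subjects is not summarised. Elsewhere SAP 4.9 states: "Area under the serum concentration curve (AUC) will be generated using the linear-log trapezoidal rule". The SAP plans no count of failures and no sensitivity analysis for Ro.

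**The concern.** Limits on fit and on percent extrapolated guard against projecting a curve beyond the data. Here the target time usually lies inside the data: anyone still quantifiable at the 96 h visit or later has samples on both sides of 48 h. The SAP's own trapezoidal rule already joins such points on the log scale.

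Whether AUCtau is kept therefore depends on the subject's own elimination curve, which is also what determines accumulation. After dose 1 the pre-dose-2 sample at 48 h is scheduled, so the denominator of Ro is normally observed while its numerator must pass a filter. PK is a secondary objective (Protocol 3.2), and with 6 active subjects per cohort a few losses can leave a dose level without a summary. Because the percentage is undefined, the person programming the analysis would decide how many subjects remain.

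**Working it through.** The documents give no half-life, assay limit, accumulation figure or expected loss, so there is no plan figure to reproduce.

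**Inputs from the documents.** tau = 48 h; 6 active subjects per cohort; 12 doses on a 48/48/72 h pattern; dose-12 samples at 0, 1, 2, 3, 4 and 8 h, 12–36 h, 48–144 h, 7 days and 28 days. The last two are taken as 168 and 672 h, from the schedule (768 − 600 and 1272 − 600). SAP 4.9 labels them 144 and 648 h.

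**Assumed inputs.** Median half-life 12–96 h with between-subject CV 50%; dose-1 Cmax/LLOQ 10, 100 or 1000; residual error 20% on the log scale; one compartment, ka 1/h; lambda from the best adjusted R-squared on at least three points after Cmax.

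**Three meanings of the percentage.**
- (a) The part of AUCtau after the last sample before 48 h.
- (b) The part of AUCinf after the last quantifiable sample.
- (c) The part of AUCtau after the last quantifiable sample, which is zero if a sample at or after 48 h is quantifiable.

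**Step 1, closed form, mono-exponential decay.** For (a) with a sample at exactly 24 h, the share is q/(1 + q), where q = exp(−24λ). At a 12 h half-life q = 0.25 and the share is 0.25/1.25 = 20.0%. At 24, 48 and 96 h it is 33.3%, 41.4% and 45.7%. Every half-life of 12 h or more then fails, and the accumulation index 1/(1 − exp(−48λ)) of those kept is below 1.067, against 1.33, 2.00 and 3.41 at 24, 48 and 96 h. The actual sampling time matters: at a 24 h half-life the share is 60.9% with the sample at 12 h and 13.8% at 36 h.

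For (b) the share is exp(−λT), where T is the last quantifiable time. It reaches 20% at a half-life of T·ln 2/ln 5, that is 10.3, 41 and 72 h for T = 24, 96 and 168 h. At a 48 h half-life it is 70.7%, 25.0% and 8.8%, so a slow eliminator still quantifiable at 7 days passes.

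**Step 2, simulation (1,500 subjects per setting).** Ranges run over the three Cmax/LLOQ values. Each cell gives the share kept and the geometric mean true Ro of those kept.

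| Median half-life | Ro, all | (a) | (b) | (c) |
|---|---|---|---|---|
| 12 h | 1.11 | 23–41%; 1.06–1.07 | 22–83%; 1.13 | 31–84%; 1.13 |
| 24 h | 1.37–1.40 | 11–20%; 1.21–1.24 | 38–94%; 1.38–1.55 | 52–95%; 1.38–1.53 |
| 48 h | 2.00–2.01 | 4–6%; 1.53–1.63 | 56–96%; 1.96–2.00 | 79–97%; 2.00–2.09 |
| 96 h | 3.18–3.24 | 1–2%; 2.13–2.35 | 50–97%; 3.15–3.43 | 85–98%; 3.18–3.28 |

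Only (a) pulls Ro clearly towards 1. At a median of 24 h the R-squared test passes 74%, 97% and 97% of the slower half (Cmax/LLOQ 10, 100, 1000) and 50%, 77% and 94% of the faster half. There it tends to lose fast eliminators.

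**Step 3, needless loss.** Among subjects with quantifiable samples on both sides of 48 h, the rule loses about 1–20% under (c), up to about 60% under (b) and about 30–99% under (a). A run at exactly the settings above gave 1–18%, 3–49% and 62–99%, inside those limits.

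**Step 4, effect on a cohort.** With retention p, P(fewer than 3 of 6) = (1−p)^6 + 6p(1−p)^5 + 15p²(1−p)^4. At a median of 24 h this is 90–98% under (a) (p = 0.20 to 0.11), 59% under (b) at its lowest retention (p = 0.38) and 31% under (c) at its lowest (p = 0.52). At the highest retention under (b) and (c) (0.94 and 0.95) it is near zero.

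**Step 5, error of interpolation.** On a curve that flattens on the log scale, a straight log-line between about 24 and 96 h lies above the curve. In the bi-exponential cases tried, C48 came out about 3–10% too high at the median. In four such examples the error in AUCtau was 0.05–5%.

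**The case against.** A reader might infer that the rule removes slow eliminators and so hides accumulation. The documents do not support that. If the last quantifiable sample is fixed at 96 h for everyone, with an assumed median half-life of 40 h and CV 50%, meaning (b) keeps 53% of subjects and gives Ro 1.44 instead of 1.77. But serum is also drawn at 7 and 28 days, and slow eliminators are the likeliest to be quantifiable then. When the last quantifiable time follows from an assay limit (initial dose-1 concentration/LLOQ 10 to 100), 73–95% are kept and Ro is 1.74–1.80.

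Other points also stand:
- The rule applies only where C48 was not collected.
- A failing subject loses the AUCtau-based parameters. Cmax, Tmax, Ctrough and Ro,Cmax remain, concentrations are still listed, and removal from the PK Population is discretionary.
- Protocol 13.8 judges steady state from troughs and allows sparse-sampling analysis.
- A terminal fit using points on both sides of 48 h already estimates C48 within the data.

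These limit what can be said about bias. They do not justify the filter. Under (c), the most lenient meaning, the R-squared test still discards values for subjects whose samples bracket 48 h, and the SAP does not say that (c) is meant.

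**Conclusion.** The point holds as a needless and undefined filter on dose-12 AUCtau, and so on Ro, Css, CL/F and V/F. It will apply to most subjects, because C48 will seldom be observed. For subjects with samples on both sides of 48 h the loss ranges from about 1% to nearly all, depending mainly on which meaning of the percentage is programmed.

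The documents do not fix the size or direction of bias in Ro. It is strongly downward under (a) and about nil or upward under (b) and (c). It would be wrong to conclude that accumulation as a whole is biased towards none. All sizes rest on the assumed half-lives, assay limits, residual error and one-compartment model. The change is worth making because it is cheap and removes this selection for bracketed subjects, whichever way it runs.

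**What to change.** Amend the footnote to Table 26 as follows:

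- When quantifiable samples lie on both sides of 48 h, obtain C48 by log-linear interpolation between them at actual times, with no R-squared or percent-extrapolated condition. This agrees with the SAP's linear-log rule.
- Use lambda, with the existing three criteria, only when the last quantifiable sample is before 48 h. State that the percentage is then the part of AUCtau beyond that sample.
- Report by dose group how many subjects fail and on which criterion. Flag AUCtau values that rest on a failing lambda, and give Ro with and without them.

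V/F contains λz and still needs an acceptable fit. Interpolation recovers AUCtau, Css, Ro and CL/F.

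The cost is one footnote, one change in the PK software set-up and a short table, with no new samples. The downside is the interpolation error across a wide gap shown above.

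### SAP 4.9: with BQL values set to 0, a BQL 48 h sample after MAD dose 1 turns the unsampled 12–48 h gap into a line to zero, which can inflate dose-1 AUCtau and give a spurious Ro below 1

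*SAP*

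**What the plan says.** The text after Table 26 in SAP 4.9 reads: "Concentrations below the limit of quantification (BQL) will be considered to be 0 concentration". It does not separate pre-dose, embedded and trailing BQL values. On the integration method SAP 4.9 says: "Area under the serum concentration curve (AUC) will be generated using the linear-log trapezoidal rule". It does not say what happens when a segment ends at zero.

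For the MAD part, Table 26 defines AUCtau at both dose 1 and dose 12 as the area "from 0 to the end of the dosing interval (tau, where tau will equal 48 hours" and the accumulation ratio Ro as "AUCtau (week 4, dose 12)/ AUCtau (week 1, dose 1". The two serum grids differ:

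- Dose 1: "Serum: 0, 0.5, 1, 2, 3, 4, 12; pre-Dose 2 (48 hours post-dose 1". Nothing is drawn between 12 and 48 h.
- Dose 12: "Serum: pre-dose (0), 1, 2, 3, 4, 8, 24, 96, 144 (7 days post-last dose". This grid has 8 h and 24 h samples.

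The footnote to Table 26 lets an uncollected C48 at dose 12 be estimated from the subject's own lambda. The conditions are at least 3 points, R-squared of at least 0.9 and less than 20% extrapolated. This is the only exception to the rule against imputing missing values, and dose 1 has no counterpart. Every PK parameter with enough evaluable subjects is to be summarised with, among other statistics, a geometric mean.

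**The concern.** A trailing BQL value means only that the concentration is somewhere below the limit. Entered as 0 at 48 h after a quantifiable 12 h sample, it fixes the shape of a 36 h segment that contains no data. A log segment to zero is undefined, and the ordinary fallback is a straight line. For a drug that has largely gone well before 48 h, that line contains much more area than the true curve.

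The same subject's dose-12 AUCtau rests on 8 h and 24 h samples and may have a lambda-estimated C48. Ro therefore divides two areas built by different rules. That asymmetry needs no assumption about half-life.

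Three results are at stake: dose-1 AUCtau, Ro, and any comparison of either across doses. Separately, one BQL Ctrough entered as 0 makes the planned geometric mean zero or undefined for that group.

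**Working it through.** The documents state no figure for half-life, LLOQ or AUC bias, so there is no plan figure to reproduce.

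**Inputs from the SAP:** BQL = 0; tau = 48 h; dose-1 times 0, 0.5, 1, 2, 3, 4, 12, 48 h; dose-12 times 0, 1, 2, 3, 4, 8, 24 h, plus C48.

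**Assumptions:** one compartment; first-order absorption (rate 1–4/h, or absorption half-life 0.25–1 h); LLOQ 1–10% of Cmax; linear-up/log-down with linear fallback to a zero; steady state at a constant 48 h interval.

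**Step 1, the 12–48 h segment after dose 1.** With C48 = 0 the area is 0.5 x 36 x C12 = 18 x C12. The true area is C12 x (1 − exp(−36λ))/λ, with λ = ln 2 / half-life. The last column is the simulated error in the whole dose-1 AUCtau when C48 is BQL and C12 is quantifiable (absorption half-life 0.5 h).

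| Half-life | True area / C12 | 18 ÷ true | Dose-1 AUCtau error |
|---|---|---|---|
| 2 h | 2.9 | 6.2 | +9% |
| 3 h | 4.3 | 4.2 | +22% |
| 4 h | 5.8 | 3.1 | +29% |
| 5 h | 7.2 | 2.5 | +31% |
| 6 h | 8.5 | 2.1 | +29% |
| 8 h | 11.0 | 1.6 | +23% |
| 12 h | 15.1 | 1.2 | +9% |
| 16 h | 18.2 | 0.99 | −1% |
| 24 h | 22.4 | 0.80 | −13% |

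The sign changes at 15.7 h. With absorption rates of 1–4/h, the error is +19 to +32% at 3–8 h and +6 to +10% at 2 h.

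**Step 2, hand check.** The error is roughly the true 12–48 h share of AUC0–48 times (ratio − 1). At 4 h the share is 13–15%, so 0.13–0.15 x 2.13 = 28–32%. At 8 h it is 35–38%, so 0.35–0.38 x 0.63 = 22–24%. Both agree with the table.

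**Step 3, Ro.** Take a 4 h half-life, absorption rate 2/h and LLOQ 1% of Cmax. Dose 1 is 1.28 x true and dose 12 is 0.99 x true, so Ro = 0.99/1.28 = 0.77 against a true 1.00. Across 4–8 h, Ro reads about 0.75–0.84 against a true 1.00–1.02.

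The 3 h result depends on the dose-12 24 h sample. If that is BQL too, the 8–24 h segment becomes 0.5 x 16 x C8 = 8 x C8 against a true 4.2 x C8. Both halves of Ro are then inflated and it reads 0.91–0.93. If the 24 h sample is quantifiable, Ro at 3 h is also in the 0.7s to low 0.8s.

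**Step 4, across doses.** Fill doses run from 6.25 to 50 mg, a factor of 8. Under linear PK, an LLOQ at 1% of Cmax for 50 mg is 8% for 6.25 mg. At an 8 h half-life C48 is about 2% of Cmax. It is then quantifiable at 50 mg (Ro about 1.01) and BQL at 6.25 mg (Ro about 0.82, dose-1 AUCtau +22%). Ro would seem to rise with dose, and dose-normalised dose-1 AUCtau to fall, only because of the BQL rule.

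**Step 5, after the fix.** Completing dose 1 with lambda z leaves its AUCtau within about 3% of true and brings Ro to about 0.95–1.01 at 3–8 h. The extrapolated 12–48 h share is 13–15% at 4 h, 20–22% at 5 h, 26–28% at 6 h and 35–38% at 8 h. Read as a share of AUC, the SAP's 20% limit is therefore passed above about 5 h.

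**The case against.** The strongest reply is that everything depends on a condition the documents cannot confirm. Protocol 2.1.4 reports no prior clinical study with the nebulised product, and no LLOQ is stated. Sampling runs to 168 h in the SAD part and to 28 days after the last MAD dose, so the design allows for a long tail. If C48 is quantifiable there is no error. Two-phase profiles (slow phase 2–20%, slow half-life 12–48 h) gave errors from −19% to +12%. This stands, and it is why the size is given only under stated assumptions.

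The reach is also limited. SAD AUClast stops at the last quantifiable value. Protocol 13.8 likewise defines AUC0-t as "Area under the curve to the final sample with a concentration greater than lower limit of quantification (LLQ", a different parameter from AUCtau, so a trailing zero inflates neither. Ro,Cmax, defined as "Cmax(week 4, dose 12)/ Cmax (week 1, dose 1", and the lambda-based accumulation index do not use dose-1 C48. Protocol 13.8 judges steady state from troughs. Escalation rests on DLTs and adverse events reviewed by the DSMC. Individual profiles are plotted, so a zero at 48 h would be visible. All of this stands. It lowers the importance of the point, but it does not make the dose-1 rule right where it applies or make the two halves of Ro comparable.

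Finally, wording cannot replace samples that were never planned between 12 and 48 h. If lambda z completion kept the 20% limit as a bar, every affected subject with a half-life above about 5 h could lose dose-1 AUCtau and Ro. That objection is correct, and the fix is adjusted for it.

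**Conclusion.** The point holds conditionally. When dose-1 C48 is BQL, C12 is quantifiable and the software falls back to linear, dose-1 AUCtau is overstated by about 20–30% for a one-compartment half-life of roughly 3–8 h. Ro then reads about 0.75–0.84 at 4–8 h, and 0.91–0.93 at 3 h if the dose-12 24 h sample is BQL as well, when the true value is about 1.0. The different treatment of the two doses and the geometric-mean problem for Ctrough do not depend on the half-life.

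A reader might infer three stronger things that the documents do not support.

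- **That the overstatement is certain.** It is absent if C48 is quantifiable. It reverses above about 16 h only if C48 is still BQL; there C48 is about 14% of Cmax, so the LLOQ would have to be higher than that.
- **That true accumulation is hidden.** Where the 20–30% error arises, linear accumulation at tau = 48 h is at most about 2%, so the result is a spurious Ro below 1. Slight real accumulation is masked around 10–12 h (true 1.04–1.07 reads 0.89–0.98). At 24 h, with C48 BQL, Ro is exaggerated (1.53 against 1.34).
- **That Ro is the trial's main exposure result or drives repeat-dose safety.** No section says so; PK is a secondary objective and Ro is summarised descriptively.

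The rule should still be changed, because it gives a wrong value in a plausible range and is easily corrected.

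**What to change.** In SAP 4.9:

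1. Set BQL before the first quantifiable sample to 0. Treat BQL after the last quantifiable sample as missing for AUCtau.
2. Complete AUCtau to 48 h from the last quantifiable point with the subject's lambda z, by the same rule at dose 1 and dose 12. Keep the 3-point and R-squared 0.9 criteria.
3. Where the extrapolated share exceeds 20%, flag dose-1 AUCtau and Ro and report them with and without those subjects, rather than dropping them.
4. Report the number BQL by dose and time point, and give no geometric mean where zeros occur.

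The cost is SAP wording and NCA settings; no visit or sample changes. The downside is that some dose-1 AUCtau and Ro values will be flagged as heavily extrapolated or will not be estimable, possibly many if the half-life exceeds about 5 h. When 12 h is the last quantifiable dose-1 sample, the slope may rest on only the 3, 4 and 12 h points, and the report should say so.
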